### **List of Abbreviations**

ERSQ – Emotion Regulation skills questionnaire. Definition on page 2

MBI – Maslach Burnout inventory. Definition on Page 2

PI – principal investigator

SICG© - Serious illness conversation guide. Defined on page 3.

## Study Summary

Title	An Education and behavioral, single-center, Observational Cohort study evaluating the effect of emotion regulation and burnout on medical trainees' Learning and Documentation of serious illness communication
Short Title	Emotion Regulation and Burnout Impact on Communication Documentation
Protocol Number	The standard protocol number used to identify this study.
Phase	n/a
Methodology	Observation cohort Study
Study Duration	Two Years
Study Center(s)	Single-center: Dartmouth-Hitchcock Medical Center
Objectives	Aim 1. Evaluate the efficacy of our multimodal communication skills training on trainee documentation, confidence and observed communication skills over 12 months. Aim 2. Test the relationship between emotion regulation, and burnout on trainee skill enactment over 12 months.
Number of Subjects	42
Diagnosis and Main Inclusion Criteria	Internal Medicine Residents and Hematology-Oncology who undergo palliative care elective AND Serious Illness Communication training
Study Product, Dose, Route, Regimen	n/a
Duration of administration	n/a
Reference therapy	No gold standard for communication skills training
Statistical Methodology	one-side proportion test with exact test for primary outcome. Secondary outcomes use different statistical tests: 1) a linear mixed model with random subject effect to test whether three different scores in simulated encounters are different; 2) summary statistics, 3) t-tests

## 1 Introduction

This document is a protocol for a human research study. This study is to be conducted according to US and international standards of Good Clinical Practice (FDA Title 21 part 312 and International Conference on Harmonization guidelines), applicable government regulations and Institutional research policies and procedures.

### 1.1 Background

Effective communication around serious illness is an essential clinical competency for all physicians. Physicians, however, often fail to disclose prognostic information and to adequately solicit patient values. Cited barriers to effective communication include insufficient physician training in communication and difficulty in dealing with patient emotion.

While formal communication skills training programs improve learners' behaviors in proximate, controlled settings (e.g., simulation), the evidence that this training has long-term impacts on learners' behavior and associated patient outcomes is limited and mostly demonstrates null effects. Human behavior can be resistant to change, and psychologic theory suggests twelve domains for why physician behavior does not change. One of these twelve domains is emotion regulation. Emotion regulation, defined as the ability to respond to ongoing demands of experience with a sufficiently flexible range of emotions, is necessary for effective prognostic disclosure, given both patient and provider have emotional reactions to such information. Burnout, a process involving emotional exhaustion, depersonalization, and low personal accomplishment, adversely impacts emotion regulation. No studies have addressed the potential role of emotion regulation and burnout as physician factors affecting the acquisition of physician communication skills.

The purpose of this study is to twofold. First, evaluate the efficacy of a communication skill training we integrated into graduate medical education by longitudinally tracking participants' documentation behavior. Second, perform exploratory analyses of physicians' emotion regulation skills and burnout as potential mechanisms for communication skill acquisition.

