### **Aim 2. Test the relationship between emotion regulation and burnout on trainee skill enactment over 12 months.**

Hypothesis: Trainees in the top half of template users will have higher a TOTAL emotion-regulation score than trainees in the bottom half (Ha2a). Trainees in the top half of template users will have lower Emotional Exhaustion scores than trainees in the bottom half (Ha2b).

Rationale: Given their high emotional content, a physician's ability to regulate their own emotions and emotional exhaustion may impact their capacity to engage in serious illness conversations. In a healthcare setting, the ESRQ was used to assess non-physician participants' competence to cope with specific and general aspects of negative emotions. We know of no studies examining its role in physicians and specifically medical trainees.

[figure not shown]
Outcomes: For ERSQ and MBI achieve complete data collection in ≥80% of willing participants (primary).

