#### **6.2 Analysis Plan**

Primary Hypothesis: Ha1a

We will calculate the proportion of trainees with template use and provide 95% confidence intervals with exact method, then we will test the hypothesis using a proportion test.

Secondary Hypotheses

Ha1b: Trainee and faculty confidence will increase after training for  $\geq 50\%$  of participants.

We define increased confidence as trainee and faculty post-intervention confidence scores of 4 or 5 on a 5-point Likert scale. We will calculate proportion of subjects who have increased confidence and show 95% confidence intervals as well, then we will use a proportion test for the hypothesis.

**Ha1c: Observed communication skills scores at the second and third simulated patient encounter will improve over the first encounter.**

The observed communication skills scores have three different scores (two sub-scores and one combined/total score). We will apply a linear mixed model with random subject effect to test whether each of three scores are different from encounter 1 to 2 and 3 separately. P-values will be adjusted for multiple tests by the Dunnett method.

**Ha2a: Trainees in the top half of template users will have higher total emotion-regulation competences (TOTAL) than trainees in the bottom.**

The ERSQ yields 10 different scales of emotion regulation: 9 specific competences and 1 TOTAL competency which is the average of the nine scales. We will provide summary statistics (mean and standard deviation) of TOTAL competency and use a two-sample t-test to test differences between the top half and low half groups of patients. P-value will be presented.

**Ha2b: Trainees in the top half of template users will have lower Emotional Exhaustion (EE) scores than trainees in the bottom half.**

We will provide summary statistics (mean and standard deviation) of EE scores and use a two-sample t-test to test differences between the top half and low half groups of patients. P-value will be presented

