### **6.3 Subject Population(s) for Analysis**

*Primary outcome is all residents and fellows trained. Secondary outcomes evaluating emotion regulation skill and burnout are in all residents and fellows who consented to be part of Tier 2 – the behavioral study part.*

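### Separate unadjusted tests of ERSQ TOTAL and Emotional Exhaustion cannot show whether emotion regulation relates to template use beyond burnout

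*Combined protocol and SAP*

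**What the plan says.** All references are to the combined protocol and SAP.

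- **Section 1.1, burnout and emotion regulation:** "Burnout, a process involving emotional exhaustion, depersonalization, and low personal accomplishment, adversely impacts emotion regulation".
- **Section 1.1, purpose of this part of the study:** to "perform exploratory analyses of physicians' emotion regulation skills and burnout as potential mechanisms for communication skill acquisition".
- **Section 2, Aim 2 rationale:** a physician's "ability to regulate their own emotions and emotional exhaustion may impact their capacity to engage in serious illness conversations".
- **Section 2, Ha2b:** "Trainees in the top half of template users will have lower Emotional Exhaustion scores than trainees in the bottom half". Ha2a makes the matching prediction of a higher ERSQ TOTAL in the top half.
- **Section 6.2, Ha2a:** summary statistics "of TOTAL competency and use a two-sample t-test to test differences between the top half and low half groups of patients".
- **Section 6.2, Ha2b:** "We will provide summary statistics (mean and standard deviation) of EE scores and use a two-sample t-test to test differences", again between the two halves.
- **Section 6.3:** these outcomes are analysed in "all residents and fellows who consented to be part of Tier 2".

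Neither section 6.2 nor the Study Summary names a covariate, a joint model or a sensitivity analysis for Aim 2. Tier 2 trainees complete the ERSQ and MBI together before training (5.1) and again at months 6 and 12 (5.6). Section 6.2 does not say which time point enters the t-tests.

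**The concern.** Section 1.1 puts burnout upstream of emotion regulation, and Ha2b links EE to template use. If EE lowers TOTAL and also lowers use by a route of its own, the top half of users will have higher TOTAL even when emotion regulation has no relation to use beyond burnout. Two separate tests would then report one burnout association as two findings.

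The interpretation is what is at stake. Section 1.1 describes emotion regulation and burnout as possible mechanisms, and the study title speaks of their effect. A report with both t-tests positive invites the conclusion that each plays its own part, and the planned analysis holds nothing that could support or refute this.

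**Working it through.** **The plan's own figure.** There is none to reproduce. The only power statement (6.1) concerns the primary hypothesis on template use.

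**Inputs.**
- From the documents: 42 trainees in all (6.1). Ha2a uses Tier 2 consenters only (6.3), so 42 is the upper limit.
- Assumed: two-sided 5% test (6.2 states no level for Ha2a); normal scores; use treated as continuous and split at the median; all correlations; Tier 2 sizes of 30 and 24 as illustrations below the limit.

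**Step 1: EE related to both TOTAL and use, with no direct TOTAL-use link.** Write a for the EE-TOTAL correlation and b for the EE-use correlation. The expected difference in TOTAL between halves, in SD units, is

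a × b × 2√(2/π) = a × b × 1.596.

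With 21 per half, the approximate chance of a significant result in the Ha2a direction is Φ(difference × √(21/2) − 1.96), where √(21/2) = 3.240.

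| a / b | Difference (SD) | Approximate chance |
|---|---|---|
| -0.3 / -0.3 | 0.09 × 1.596 = 0.144 | Φ(0.466 − 1.96) = 7% |
| -0.5 / -0.3 | 0.15 × 1.596 = 0.239 | Φ(0.775 − 1.96) = 12% |
| -0.5 / -0.5 | 0.25 × 1.596 = 0.399 | Φ(1.293 − 1.96) = 25% |
| -0.7 / -0.5 | 0.35 × 1.596 = 0.559 | Φ(1.811 − 1.96) = 44% |

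Simulation (at least 20,000 replicates per cell, two-sided 5%) agrees:

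| a / b | n=42 | n=30 | n=24 | With EE in the model |
|---|---|---|---|---|
| -0.3 / -0.3 | 7% | 6–7% | 6% | about 5% |
| -0.5 / -0.3 | 11–12% | 10% | 8–9% | about 5% |
| -0.5 / -0.5 | 24–25% | 18% | 15% | about 5% |
| -0.7 / -0.5 | 44% | 32% | 26% | about 5% |

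When a = 0, the unadjusted test also rejects in about 5% of trials, so the excess comes entirely from EE.

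**Step 2: a chain, in which burnout acts on use only through emotion regulation.** Assume a TOTAL-use correlation of 0.5 and no direct EE path, at n=42. The expected unadjusted difference is 0.5 × 1.596 = 0.80 SD (0.78 in simulation), with 77% power.

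| EE-TOTAL | Adjusted difference (SD) | Adjusted power |
|---|---|---|
| -0.5 | 0.61 | about 64% |
| -0.7 | 0.43 | about 48% |

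At n=30 with EE-TOTAL of -0.7, power falls from 61% to about 34%. The loss comes from a smaller adjusted difference. The standard error does not grow materially.

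**Reading the two steps together.** The unadjusted difference cannot distinguish Step 1 from Step 2. The adjusted difference is about zero in Step 1 and positive in Step 2, but with reduced power.

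**The case against.** The strongest reply is that Ha2a claims no independent link. It says only that TOTAL is higher in the top half. If EE lowers both TOTAL and use, the halves do differ in TOTAL and Ha2a is true. A reader might take the 7% to 44% as false-positive rates, or conclude that the t-test is the wrong test of Ha2a. The documents support neither reading: the rates are power to detect a real marginal difference, and the test is valid for the hypothesis as written. This stands.

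A reader might also infer that the plan's own theory makes EE a common cause of TOTAL and use. That goes too far. Section 1.1 treats emotion regulation as necessary for good prognostic disclosure and burnout as harming it, which fits a chain equally well, and in a pure chain EE does not confound Ha2a. A separate EE path rests on the Aim 2 rationale, which is hedged and can even be read as referring to the ability to regulate both emotions and exhaustion. Ha2b is an association and fits either structure. This also stands: EE alone is a possible explanation of a positive Ha2a, not the one the plan asserts.

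Finally, the analyses are called exploratory, no passage promises to separate the two factors, and every correlation used here is assumed. That lowers the weight of the point but does not answer it. The plan offers both factors as possible mechanisms, and two marginal tests cannot tell one association from two.

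**Conclusion.** The point holds as a limit on interpretation. The Ha2a t-test may stay. With the separate EE test beside it, it still cannot show whether emotion regulation is related to template use beyond burnout.

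Under assumed correlations and no direct TOTAL-use link, a significant Ha2a arises in about 7% (-0.3/-0.3) to 44% (-0.7/-0.5) of trials at n=42, and less often with fewer Tier 2 consenters. With EE in the model the rate is about 5%. These figures rest on normal scores, continuous use, a two-sided 5% test and EE measured without error. Error in measuring EE would leave some of its influence in the adjusted estimate.

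Severity: consider. The analyses are exploratory and the remedy is cheap.

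**What to change.** In section 6.2, keep the two-sample t-test as the test of Ha2a and leave Ha2b as planned. Add an exploratory linear model of baseline TOTAL on user half plus baseline EE, and report the adjusted difference with a 95% CI beside the unadjusted one. State that the baseline ERSQ and MBI scores are used, since 6.2 now leaves the time point open.

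Add a rule for interpretation: describe emotion regulation as having a role separate from burnout only if the adjusted estimate supports it, and do not read a null adjusted result as evidence of no role.

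The cost is a few sentences, one model and one degree of freedom. No new data are needed, because both scores come from the same Tier 2 trainees before training. The real price is the loss of power if burnout acts only through emotion regulation, which is why the adjusted result should be supplementary.

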### 1.2 Study Assessment Tools

Confidence Survey – Using a 5 point Likert scale (i.e. 1=strongly disagree, 2=disagree, 3=neutral, 4=agree 5=strongly agree) participants were asked to rate their confidence in various communication skills domains pre- and post-intervention via online survey.

Emotion Regulation Skills Questionnaire (ERSQ) – This validated instrument consists of 27 items, and includes subscales related to nine competencies of coping with negative emotion (awareness, sensations, clarity, understanding, acceptance, tolerance, readiness to confront, compassionate self-support and modification) which can be summed to a total score (TOTAL). The ERSQ assesses each skill by means of three items introduced by the phrase "In the last week..." and answered on a 5-point Likert-scale. Higher scores indicate stronger emotion regulation skills. We will administer the ERSQ via online survey.

Maslach Burnout Inventory™(MBI) – This validated, psychological inventory consists of 22 items related to occupational burnout, and includes subscales related to Emotional exhaustion (EE; 9 items), Depersonalization (DP; 5-items), and Personal Accomplishment (PA; 8 items). The MBI assesses each item on a 7-point Likert-scale. Higher scores indicated greater burnout. . We will use the MBI / Human Services Survey for Medical Personnel administered via online survey.

Semi-structured interview – At 6 months, participants (e.g. trained faculty, residents, and fellows) are asked a series of preselected questions in a one-on-one interview about their experience with the training, using the SICG with patients, benefits and difficulties of the training in the clinical setting.

**Serious Illness Conversation Guide (SICG©)** – improve the timing, frequency, quality, and tolerability (for both patient and clinician) of patient-centered values and goals conversations for patients living with serious illness. The SICG© was co-produced by clinicians, patients, and families and is a checklist of best-practice communication steps for use in patients with serious illness.

**Skills acquisition checklist** - used by independent observer during simulated patient encounters to evaluate trainees. One point is assigned for each item used by the trainee. The checklist contains three scores: conversation guide specific items (16 points), global communication skills (9 points), and a combined score (25 points). This checklist was developed internally and based on the experience training residents in the Serious Illness Conversation Guide (SICG).

**Template Use** –The analytics team at our institution is able to link the smartform to the physician who made alterations, the content of those alterations, patient and date of change.

### **1.3 Study Systems-based Interventions**

**Audit and profile feedback** –*Injunctive norms messaging with social comparisons* is used to change attitudes by communicating approval or disapproval of behavior. This acknowledges that people make decisions based on social cues, self-image, local values and identities. We also leverage pre-commitment contracts. Trainees will receive their personal template use frequency compared to top performers via email. Non-top and top performers will receive different messages, customized through pre-testing with non-study residents and fellows. For example: “Talking to patients about their values is important but can take some pre-visit planning. Choose a patient you will see in the next two weeks to use the SICG” (non top-performers) or “Good job! Talking to patients about their values is important. The way we continue to improve is by having more conversations. Choose a patient you will see in the next two weeks to use the SICG.” (top-performers).

**Priming** – Priming physicians to reflect on whether their patients have serious illness is associated with more goals-of-care discussions. Using the chart review, we will generate a list unique to each trainee enriched for outpatients with a high likelihood of having serious illness. After completing the first training session, each trainee will review their list and be asked four “yes or no” questions: 1) “Does this patient have serious illness?; 2) “Would you be surprised if this patient died in the next 12 months?;” 3) Would this patient benefit from a serious illness guide conversation?; 4) If you saw this patient again, would you use the serious illness conversation guide with him/ her?

**Template** – We designed a template to standardize SICG documentation and embedded it in the medical record. This template exists in two forms: a “dotphrase” (user enters text in a note to display template) and as a central smartform where patient responses can be recorded.

### **1.4 Prior Work**

Starting in 2017, we designed and implemented annual communication skills training. We trained 16 internal medicine residents (hereafter referred to as residents), 6 hematology-oncology fellows (hereafter referred to as fellows), and used a train-the-trainer model to train faculty attendings to serve as trainers in the clinical setting with trainees: 5 hospitalists, 4 primary care and 4 oncologists. We designed and embedded a template into the electronic medical record to standardize the documentation of the SICG. We developed a structured chart review protocol to identify outpatients with a high-likelihood of serious illness and evaluate trainee documentation habits

## 2 Study Objectives

### **Aim 1. Evaluate the efficacy of our multimodal communication skills training on trainee documentation, confidence and observed communication skills over 12 months.**

Hypotheses: Template use for both trainee subgroups will increase from zero after training for ≥50% of trainees (Ha1a). Trainee and faculty confidence will increase after training for ≥50% of participants (Ha1b). Observed communication skills scores at the second and third simulated patient encounter will improve over the first encounter. (Ha1c).

Rationale: Augmenting standard training with priming, structured documentation templates, documentation audit and feedback, and embedded faculty coaches, we hope to increase the effect of communication skills training on clinical behavior change.

Outcomes: Participant template use at 12 months (Primary). Trainee, post-intervention self-rated confidence and performance in simulated patient encounters (Secondary).

### **Aim 2. Test the relationship between emotion regulation and burnout on trainee skill enactment over 12 months.**

Hypothesis: Trainees in the top half of template users will have higher a TOTAL emotion-regulation score than trainees in the bottom half (Ha2a). Trainees in the top half of template users will have lower Emotional Exhaustion scores than trainees in the bottom half (Ha2b).

Rationale: Given their high emotional content, a physician's ability to regulate their own emotions and emotional exhaustion may impact their capacity to engage in serious illness conversations. In a healthcare setting, the ESRQ was used to assess non-physician participants' competence to cope with specific and general aspects of negative emotions. We know of no studies examining its role in physicians and specifically medical trainees.

[figure not shown]
Outcomes: For ERSQ and MBI achieve complete data collection in ≥80% of willing participants (primary).

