## 4 Subject Selection and Withdrawal

### 4.1 Inclusion Criteria

All second-year internal medicine residents. All first-year hematology-oncology fellows.

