### **6 Statistical Plan**

#### **6.1 Sample Size Justification**

Primary Hypothesis: Template use for both trainee subgroups will increase from zero after training for  $\geq 50\%$  of trainee (Ha1a)

Let null hypothesis Hnull1a be  $p < 50\%$  and alternative hypothesis be Ha1a be  $p = p_1 \geq 50\%$ , where p is proportion of trainees who have any documented template use. Sample size of 42 (12 fellows and 30 eligible residents who have completed the education intervention by the end of the grant award period [June 2020]) enables us to have Minimum Detectable Difference (MDD) 19.05%, i.e., the least p1 is 69.05%, with 80% of power and 2.5% significance level using one-side proportion test with exact test.

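### Ha2a and Ha2b compare top and bottom halves of template users without accounting for trainee type or follow-up time, leaving the comparison open to confounding; a cheap change to an exploratory aim would remove the trainee-type part.

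*Combined protocol and SAP*

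**What the plan says.** Section 2 (Aim 2) states two directional hypotheses. Ha2a is that "Trainees in the top half of template users will have higher a TOTAL emotion-regulation score than trainees in the bottom half". Ha2b is that "Trainees in the top half of template users will have lower Emotional Exhaustion scores than trainees in the bottom half".

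For each, section 6.2 gives means and standard deviations and will "use a two-sample t-test to test differences between the top half and low half groups of patients" (the people compared are trainees). It names no covariate, stratum, significance level or sidedness for these tests.

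Section 6.3 sets the population: "Secondary outcomes evaluating emotion regulation skill and burnout are in all residents and fellows who consented to be part of Tier 2". Section 4.1 shows that this population has two kinds of trainee: "All second-year internal medicine residents. All first-year hematology-oncology fellows". Section 6.1 gives the most there can be of each: "12 fellows and 30 eligible residents who have completed the education intervention".

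The measure that ranks trainees into halves is not defined. Section 1.3 speaks of a frequency when it describes the feedback emails, but neither Aim 2 nor section 6.2 says what is counted, over what time, or whether the halves are formed overall or within trainee type. Section 3.1 plans 12 months of follow-up for each participant. Section 4.4.2 ends documentation follow-up at the last day of employment for those who leave the institution.

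**The concern.** Aim 2 is about the trainee: whether skill in regulating emotion, or exhaustion, goes with putting the training into practice. Residents and fellows differ in specialty and in stage of training, and the primary hypothesis already names them as two subgroups. If one type uses the template more, it will be over-represented in the top half. If that type also scores differently on the ERSQ or on Emotional Exhaustion for reasons unrelated to template use, the t-test will credit that difference to template use.

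The error can go either way. It can produce an apparent association where there is none, or shrink a real one. For Ha2b, for example, more frequent use by more exhausted fellows would work against the hypothesised direction.

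Shorter observation raises a related problem. A trainee who leaves early has had less time to use the template and, on a total, would tend to be ranked low for that reason alone.

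**Working it through.** The plan states no power or effect size for Ha2a or Ha2b, so there is no figure to reproduce. The check asks how large the bias could be.

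**Inputs from the documents.** 12 fellows and 30 residents (section 6.1), all taken to be in Tier 2. This is an upper bound, because section 6.3 limits the analysis to those who consented. The halves are then 21 and 21.

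**Assumed inputs, not in the documents.**
- R, the fellow:resident ratio of expected template use.
- D, the fellow minus resident mean score, in SD units.
- Two-sided 5% tests.
- Overdispersed (gamma-Poisson) counts with a resident mean of 3, and ties broken at random.

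**Formula.** Let k be the number of fellows in the top half. With no association between use and score within type, the expected top-minus-bottom difference is

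bias = D × [k − (12 − k)] / 21 = D × (2k − 12) / 21.

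It is zero when D = 0. It is also zero when k = 6, which is the average when R = 1.

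**Numbers put in.** The average k comes from simulation (20,000 runs per setting):
- R = 2, k = 7.76: (15.52 − 12)/21 = 0.168. Times 0.5 gives 0.08; times 0.8 gives 0.13.
- R = 4, k = 9.26: (18.52 − 12)/21 = 0.310. Times 0.5 gives 0.16; times 0.8 gives 0.25.
- All 12 fellows on top: 12/21 = 0.571. Times 0.5 gives 0.29; times 0.8 gives 0.46.

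**Simulated results, pooled halves and plain t-test, no true association:**

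| R | D | Spurious difference (SD) | False positives |
|---|---|---|---|
| 1 | 0.5 or 0.8 | about 0 | 5.0%, 5.2% |
| 2 | 0.5 | 0.09 | 6.0% |
| 2 | 0.8 | 0.13 | 6.6% |
| 4 | 0.5 | 0.16 | 7.7% |
| 4 | 0.8 | 0.25 | 11.2% |
| 8 | 0.5 | 0.21 | 9.9% |
| 8 | 0.8 | 0.33 | 16.5% |

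In the limit with all 12 fellows on top, false positives are about 13% at D = 0.5 and 28% at D = 0.8 (10,000 runs). With D = 0 there is no bias at any R.

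**Halves formed within type (6 and 6 fellows, 15 and 15 residents), with type in the model.** The spurious difference is within 0.01 SD of zero and false positives are 4.7 to 5.3% in every setting.

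**When a true association exists.** Assume a correlation of 0.4 within type between the score and the underlying propensity to use the template, and R = 4. The within-type analysis finds a difference of 0.54 SD and rejects in about 43% of runs. The pooled analysis finds 0.34 SD at D = −0.5 (rejects in 19%), 0.50 SD at D = 0 (37%) and 0.65 SD at D = +0.5 (56%).

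**Scale.** With 21 against 21, the smallest difference detectable with 80% power is 0.89 SD.

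The effect of shorter follow-up was not quantified, because the documents give no number of leavers.

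**The case against.** The strongest reply is that the concern rests on silence and on assumed inputs. Confounding by trainee type needs template use to differ by type and also the ERSQ or exhaustion score to differ by type. The documents report neither. Section 4.1 gives only specialty and training year. The metric is undefined, so the halves could still be formed sensibly. The biases in the moderate scenarios are small beside a detectable difference of 0.89 SD. Section 1.1 calls these analyses exploratory, and Aim 2's own primary outcome is completeness of ERSQ and MBI collection, so no main claim of the study depends on the tests.

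Most of this stands, and it limits the point. A reader might infer several stronger things that the documents do not support:
- That the ranking uses raw counts. No passage says so.
- That fellows see more seriously ill patients and so will fill the top half. This is plausible from the specialty but is stated nowhere.
- That the template can be used only for seriously ill patients. The guide is meant for them, but section 1.3 describes no restriction on access.
- That the comparison is in fact confounded, or that a true association would be reversed. The adverse case above shrinks 0.54 SD to 0.34 SD, which is attenuation, not reversal.

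What does not stand is the suggestion that this is only a missing detail. The plain reading of sections 6.2 and 6.3 is one pooled group and one unadjusted test. Followed as written, that test cannot separate trainee type from template use, and a better method is available at almost no cost.

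**Conclusion.** The point holds as an exposure to confounding that the plan leaves uncontrolled; it does not show that the result will be wrong. With 12 fellows and 30 residents all in Tier 2, a use ratio of 2 to 4, a score difference of 0.5 to 0.8 SD and no true association within type, the spurious difference is about 0.1 to 0.25 SD and the false-positive rate about 6 to 11%. Larger figures need nearly all fellows in the top half. A score difference opposite in sign to a true association would weaken it. All of these sizes depend on assumed caseload and score differences. The primary endpoint is unaffected. I would rate this a cheap improvement to an exploratory aim, of low severity.

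**What to change.** In section 6.2, for Ha2a and Ha2b:
- Define template use for the split as uses per month followed, so that leavers are not ranked low for lack of time.
- Form the top and bottom halves separately among residents and among fellows, with a stated rule for ties, then combine the two top halves and the two bottom halves.
- Compare TOTAL and Emotional Exhaustion between halves in a linear model with trainee type as a term, in place of the two-sample t-test.

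The data needed should already be held: trainee type is known, section 1.2 says template entries can be linked to the physician and date, and follow-up time comes from the training date and, for leavers, the last day of employment. The cost is one degree of freedom (39 in place of 40 with all 42 trainees) and halves of at most about 6 fellows, fewer if some decline Tier 2.

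I would not divide use by the size of the chart-review list, although section 1.3 says "we will generate a list unique to each trainee enriched for outpatients with a high likelihood of having serious illness". Under section 5.2 that list covers patients the trainee had already written a note on, and review is limited to 30. Section 3.1 also lets participants decline priming. The list does not measure opportunity over the following 12 months.
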